12.5 Adverse Event Reporting

At each study visit (including unscheduled visits), the investigator, or designee, will determine whether any AEs have occurred. AEs will be reported in the patient's medical record and on the AE case report form (CRF) page and each will be classified according to the criteria in [Section 12.1](#) and [Section 12.2](#). If known, the diagnosis should be recorded, in preference to the listing of individual signs and symptoms. Any pre-existing conditions that are detected as part of the initial screening procedures will need to be reported in the medical history and not as an AE. However, pre-existing conditions that worsen enrollment should be reported as an AE.

Adverse events will be reported to FDA in accordance with the requirements outlined in 21 CFR §312.32. Deaths due to cancer progression will not be reported as expedited events. The Investigator will continue to monitor the patient until any new, changed, or worsened AE resolves, returns to baseline, or until the Investigator and Immune Design agree that follow-up is no longer necessary. AEs must be followed until resolution whenever possible.

12.6 Serious Adverse Event Reporting

If an SAE occurs, Immune Design must be notified within 24 hours of awareness of the event by the investigator. If the SAE is fatal or life-threatening, Immune Design must be notified immediately, irrespective of the extent of available AE information. In the rare event that the investigator or designee does not become aware of the occurrence of a SAE immediately, the investigator or designee must report the event within 24 hours of their awareness and document the time of when his/her first awareness occurred. For all SAEs, the investigator or designee is obligated to pursue and provide information to Immune Design in accordance with the timeframes for reporting specified above. In addition, an investigator may be requested to obtain specific additional follow-up information in an expedited fashion. This information may be more detailed than that captured on the AE CRF. In general, this will include a description of the AE in sufficient detail to allow for a complete medical assessment of the case and independent determination of causality.

New SAEs experienced by patients during the Screening Period (pre-study treatment) will be reported to Immune Design if the events are considered related to study procedures. New SAEs determined to be related to study tests or procedures (not including cancer-related events) and any hospitalizations that are experienced by patients from the time of signing the informed consent until Day 0 (start of G100 treatment) will be noted on the SAE form and CRF. From Day 0 until the EOS / Post Vaccination Safety Visit, any new SAE will be noted on the SAE form and CRF. After the EOS / Post Vaccination Safety Visit, any SAE that comes to the

attention of the site staff that may be causally related to study drug (i.e., there is a reasonable possibility that the event may have been caused by the drug) will be reported to Immune Design.

For patients receiving pembrolizumab, any SAE, or follow up to an SAE, including death due to any cause other than progression of the cancer under study that occurs through 90 days following cessation of treatment, or 30 days following cessation of treatment if the subject initiates new anticancer therapy, whichever is earlier, must be reported within 24 hours to the Sponsor either by electronic media or paper.

SAEs will be monitored until they have resolved, returned to baseline, or they are not clinically significant, stable, or do not require additional follow-up, as judged by the Investigator and Immune Design.

The SAE contact and reporting information are provided in [Appendix E](#).

12.7 Pregnancy

Sexually active men and FCBP must use an effective method of birth control during the course of the study, in a manner such that risk of failure is minimized. Before enrolling FCBP in this clinical trial, all FCBP must be advised of the importance of avoiding pregnancy during trial participation and the potential risk factors for an unintentional pregnancy. All patients (men and women) must sign an informed consent form documenting this discussion. (See conception warnings for pembrolizumab, [Sections 8.1.9 – 8.1.11](#))

All FCBP must have a negative pregnancy test within 7 days for Parts 1, 2, or 3 and within 72 hour for Parts 4 and 5 prior to the study regimen initiation. If the pregnancy test is positive, the subject must not be enrolled in the study.

In addition, all FCBP should be instructed to contact the investigator immediately if they suspect they might be pregnant (e.g., missed or late menstrual period) at any time during study participation.

If following initiation of study dosing, it is subsequently discovered that a trial subject is pregnant or may have been pregnant within one month before or after study regimens will be permanently discontinued and the patient will be followed as possible by the investigator or designated health care professional to determine pregnancy outcomes for both mother and baby. If a male patient enrolled in study has a female sexual partner who becomes pregnant after initiation of study, then the study subject should be asked permission for the investigator (or designated health care professional) to approach his partner for permission to follow-up with the pregnant partner to determine outcomes for both mother and baby.

For patients receiving pembrolizumab, it is the responsibility of investigators or their designees to report any pregnancy or lactation in a subject (spontaneously reported to them) that occurs during the trial or within 120 days of completing the trial or 30 days following cessation of

treatment if the subject initiates new anticancer therapy, whichever is earlier. All subjects who become pregnant must be followed to the completion/termination of the pregnancy. Pregnancy outcomes of spontaneous abortion, missed abortion, benign hydatidiform mole, blighted ovum, fetal death, intrauterine death, miscarriage and stillbirth must be reported as serious events (Important Medical Events). If the pregnancy continues to term, the outcome (health of infant) must also be reported. Such events must be reported within 24 hours to the Sponsor either by electronic media or paper.

12.8 Events of Clinical Interest /Medical Events of Interest

Selected non-serious and serious AEs that may be associated with G100 or pembrolizumab are also known as ECI / MEOI and must be reported to the Sponsor.

For the time period beginning when the consent form is signed until treatment allocation/randomization, any ECI, or follow up to an ECI, that occurs to any subject must be reported within 24 hours to the Sponsor if it causes the subject to be excluded from the trial, or is the result of a protocol-specified intervention, including but not limited to washout or discontinuation of usual therapy, diet, placebo treatment or a procedure.

For the time period beginning at treatment allocation/randomization through 30 days following cessation of treatment, any ECI, or follow up to an ECI, whether or not related to the Sponsor's product, must be reported within 24 hours to the Sponsor, either by electronic media or paper. Electronic reporting procedures can be found in the electronic data capture (EDC) data entry guidelines. Paper reporting procedures can be found in the Investigator Trial File Binder (or equivalent).

For G100, ECI / MEOIs may be added to the Investigator Brochure as clinical experience with G100 increases and will be used to capture additional information on these events of interest.

For Pembrolizumab, Events of clinical interest for this trial include:

- 1) an overdose of Sponsor's product, as defined in [Section 12.1 - Definition of an Overdose for This Protocol and Reporting of Overdose to the Sponsor](#), that is not associated with clinical symptoms or abnormal laboratory results.
- 2) an elevated AST or ALT lab value that is greater than or equal to 3X the upper limit of normal and an elevated total bilirubin lab value that is greater than or equal to 2X the upper limit of normal and, at the same time, an alkaline phosphatase lab value that is less than 2X the upper limit of normal, as determined by way of protocol-specified laboratory testing or unscheduled laboratory testing.*

*Note: These criteria are based upon available regulatory guidance documents. The purpose of the criteria is to specify a threshold of abnormal hepatic tests that may require an additional evaluation for an underlying etiology. The trial site guidance for assessment and

follow up of these criteria can be made available. It may also be appropriate to conduct additional evaluation for an underlying etiology in the setting of abnormalities of liver blood tests including AST, ALT, bilirubin, and alkaline phosphatase that do not meet the criteria noted above. In these cases, the decision to proceed with additional evaluation will be made through consultation between the study investigators and the Sponsor Clinical Director. However, abnormalities of liver blood tests that do not meet the criteria noted above are not ECIs for this trial.

12.9 Data Monitoring Committee

A DMC will be established to provide independent review of safety data and to assure that the risk to patients is minimized. The DMC will be composed of 2 oncologists. The DMC will review all related and unexpected (i.e., expedited) SAEs and DLTs as individual cases arise and will perform periodic reviews of all AEs, laboratory results, and patient discontinuations.

Safety data will be collected and monitored on an ongoing basis throughout the study. Immune Design will summarize all available safety and laboratory data on all patients at regular intervals (at least every 3 months) during the study, as specified in the DMC charter. Immune Design and the DMC will conduct separate reviews of these data for any safety trends that might impact the treatment of patients. Safety issues that arise out of such ongoing reviews could lead to modifications of the treatment program.

The DMC may convene on an ad-hoc basis to evaluate any urgent safety issues. Upon request, the DMC will be granted access to any available data pertinent to the issues under evaluation. Immune Design will provide cumulative data, as specified in the DMC charter, to the DMC for review, including clinical laboratory values, AEs, SAEs, medical events of interest, and patient discontinuations.

13.0 PROTOCOL DEVIATIONS

A protocol deviation is any change, divergence or departure from the study design or procedures defined in the protocol.

Important protocol deviations are a subset of protocol deviations that might significantly affect the completeness, accuracy, and/or reliability of the study data or that might significantly affect a subject's rights, safety or wellbeing such as enrolling subjects in violation of key eligibility criteria or failing to collect data necessary to interpret primary endpoints, the PI prescribing or administering the wrong dose, or the study subject being scheduled to return for follow-up intervention outside the protocol-dictated window as a convenience to the patient or study staff.

There will be unforeseen circumstances that are beyond the investigator's control (e.g., a patient not attending a scheduled follow-up visit). Prior approval will not be granted in these situations, but the investigator should report these events upon determining that a deviation has occurred.

The investigator is responsible for complying with and adhering to IRB procedures for reporting protocol deviations and violations. All protocol deviations should be documented and forwarded to Immune Design or its authorized representative.

Protocol deviations will be collected during the study, and reported by Immune Design or its authorized representative to the FDA and IRBs yearly in the annual report. Participating investigators will receive regular updates regarding their site's deviations.

14.0 STATISTICAL CONSIDERATIONS

14.1 Study Endpoints

The study endpoints include both clinical safety and immunogenicity. Where possible, parameters will be quantified for direct comparisons among the five study groups; however, due to the small sample size and the primary objective to evaluate vaccine safety and immunogenicity, all analyses will be exploratory in nature.

14.2 Sample Size

In Part 1, Part 2, and Part 3, up to 65 evaluable patients will be enrolled. In Part 1, Dose Escalation, a total of two pre-defined dose levels will be studied (see [Section 4.1](#)). For cohort 1, each patient will receive a total of 6 planned injections and up to 3 additional injections depending on the treated tumor response. A conventional “3+3” design will be used during Part 1 for dose assessment and escalation. The first cohort of 3 patients will be enrolled at the lowest dose level. If 0/3 patients experience DLT, the next cohort will be enrolled into the next higher dose. If 1/3 patients experience DLT, the current dose level will be expanded to a total of 6 patients. If 1/6 patients experience DLT, dose escalation may occur. If 2 or more patients in dose cohort experience DLT at any time, the MTD has been exceeded. The MTD or maximum safe dose (if at the highest dose level) is defined as the highest dose in which less than one third of patients in the cohort experienced a DLT.

Once the MTD or maximum safe dose examined in the study has been determined, Part 2 will begin. In the optional Large Tumor group, up to 4 patients will be treated and safety will be examined.

In Part 2, Patient Expansion, up to 24 patients (12 per treatment group) will be randomly assigned to receive treatment with either G100 alone or the sequential administration of G100 and pembrolizumab. The dose of G100 will be the MTD / maximum safe dose determined in Part 1. This portion of the study will provide additional safety, immunogenicity and early efficacy data of G100 at the MTD / maximum safe dose and provide initial data on the sequential administration of G100 and pembrolizumab. This analysis is designed to be exploratory but will provide important data to guide further development. While the sample size is not based on formal power calculations, it is expected to provide adequate preliminary data to inform subsequent trials and to reject an indication should no clinical benefit occur. For example, if the

Immune Design**G100 (GLA-SE) and Pembrolizumab or Rituximab****Protocol IMDZ-G142; Version 04B; November 15, 2018**

true ORR is 20%, we will conclude futility with a 6.9% error rate if 0 response is observed in 12 patients. In that case, the Sponsor would terminate that study arm for development.

In Part 3, G100 Expansion of 20 μ g Dose Group, up to 25 patients will be enrolled and treated with intratumoral G100 at 20 μ g/dose following radiation therapy. The purpose of this group would be to explore the safety and potential clinical responses at the higher dose level. The number of patients was chosen to provide a similar cohort treated with G100 alone in Parts 1 and 2 for descriptive comparison. In those portions of the study, 18 patients (3 at 5 μ g/dose; 15 at 10 μ g/dose) may receive intratumoral G100 alone following radiation therapy.

In Part 4, G100 Plus Pembrolizumab, at least 22 evaluable patients will be enrolled and treated as part of a Dose Escalation group or a Patient Expansion group with intratumoral G100 in combination with pembrolizumab. The purpose of this treatment regimen will be to explore the safety and preliminary clinical efficacy and biomarker changes of patients treated with G100 at a dose of 20 μ g/lesion injected in single or multiple lesions. The administered dose of G100 will depend on the number of potentially injectable lesions and whether the MTD has been established during Dose Escalation. One or more lesions will be targeted for injection and each lesion would receive 20 μ g of G100 intratumorally (or 10 μ g G100 if 20 μ g/lesion in a single lesion is not tolerated) as long as the total number of treated tumor lesions and total systemic dose does not exceed the MTD (if established) or 80 μ g total dose (20 μ g injected in 4 lesions). This analysis is designed to be exploratory and will evaluate safety, clinical outcome and exploratory biomarkers to guide further clinical development. Clinical efficacy including ORR and DOR will be evaluated in relapsed or refractory FL patients who received ≥ 3 prior systemic therapies.

For this analysis, 22 efficacy evaluable patients will be required. Efficacy evaluable patients are patients who received at least 3 doses of G100 at 20 μ g/lesion and at least 1 dose of pembrolizumab, had at least one post baseline tumor assessment, and had no major protocol deviations that impact the efficacy of the study treatment or the assessment of response. Patients who received G100 20 μ g/lesion during Dose Escalation in Part 4 may be included in clinical response analysis. With a target ORR of 40%, if ≤ 5 responders are observed among 22 evaluable patients, we will conclude futility with 7.2% error rate. The Sponsor will use this analysis to decide whether to continue further development of this regimen. Early acceptance of treatment at the end of the 22 evaluable patients is not permitted. If the true ORR for this group is 20% and 20% ORR is considered not clinically meaningful, the probability of observing $\leq 5/22$ responders and stopping the study is 73.3%.

In Part 5, G100 Plus rituximab, after Dose Escalation has been completed, patients will be treated with intratumoral G100 at the recommended dose level in combination with rituximab. The purpose of this Patient Expansion group will be to explore the safety and clinical outcome of patients treated at a biologically active and safe G100 dose level administered into single tumor lesion in combination with rituximab. This analysis is designed to be exploratory and will evaluate safety, clinical outcome and exploratory biomarkers.

An exploratory analysis will be performed on 20 efficacy evaluable relapsed or refractory FL patients and will include analyses of the frequency and duration of CRs. Efficacy evaluable patients are patients who received at least 3 injections of G100 at the recommended dose and 3 doses of rituximab, had at least one post baseline tumor assessment, and had no major protocol deviations that impact the efficacy of the study treatment or the assessment of response. Five or more CRs in 20 patients treated with G100 plus rituximab will signal an improvement of CR rate over 10%. For reference, the probability of observing ≤ 4 CRs in 20 patients is 5.1% if the true CR rate is 40% (the targeted CR rate). Patients who received G100 at the recommended dose during Dose Escalation in Part 5 may be included in clinical response analysis. With 20 efficacy evaluable patients, and a historical CR rate of 10%, assuming a true CR rate of 32% in the G100 plus rituximab, this subgroup analysis has 82% power to detect a signal of an improvement in CR from 10% at a 1-sided alpha of 0.05.

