As much of the full dose as possible should be given and the total dose of G100 administered should be recorded for each administration. As noted above, it should be expected that there will be peritumoral administration of G100 from either direct or extravasation following injection. In Parts 1 to 4, if the tumor mass has not regressed completely following 6 doses, treatment may continue for 3 additional weekly intratumoral doses (9 total). At the discretion of the investigator, should the G100 treated lesion(s) become too small or inaccessible for injection, G100 therapy will stop and the patient will continue to be followed for tumor response at distal sites and for long-term clinical status. In Part 5, up to 6 doses will be administered.

For All Parts (1 to 5)

Retreatment / Second Course: Patients may be eligible to receive a second course of G100 if they achieved SD or better or have PD that does not require immediate therapy, have accessible and injectable lesions outside the prior radiation field, and have not had significant treatment emergent AEs (including events that would be considered a DLT) as determined by the investigator and the Sponsor. For patients enrolled on Parts 4 or 5, the same previously injected tumor sites may be targeted or a replacement site(s) may be chosen.

Six weeks or more after completion of the first course of G100 treatment, the second course would begin and consist of G100 alone (no radiation and no additional rituximab) at the same dose received during the first course of therapy. Treatment would be administered on a similar weekly schedule as the first course except without radiation therapy (or rituximab therapy). G100 will be injected intratumorally beginning on Day 0 (instead of Study Day 2), a second dose

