10.3.17 Visit 4: G100 Dose #2 (Day 5-7)

Patients will return for the second dose of G100 on either Day 5, 6, or 7. Note that on each immunization day, all procedures and blood draws must be done before dosing. The following will be completed:

- 1) Review of AEs and SAEs
- 2) Recording of any previous / concomitant medications
- 3) Vital signs
- 4) Symptom-directed physical exam
- 5) Assessment and measurements of tumor treated with G100 and measureable untreated distal tumor lesions by exam
- 6) ECOG status
- 7) Safety labs as in [Section 10.3.2](#) – Hematology, Clinical chemistry
- 8) G100 administration

10.3.18 Visits 5, 6, 7, 8: G100 Doses #3, 4, 5, 6 (Days 14, 21, 28, 35)

Patients will return for their G100 doses #3, 4, 5, and 6. Note that on each immunization day, all procedures and blood draws must be done before dosing. The following will be completed:

- 1) Review of AEs and SAEs
- 2) Recording of any previous / concomitant medications
- 3) Vital signs
- 4) Symptom-directed physical exam
- 5) Assessment and measurements of tumor treated with G100 and measureable untreated distal tumor lesions by exam
- 6) ECOG status
- 7) Safety labs as in [Section 10.3.2](#)– Hematology, Clinical chemistry
- 8) Pharmacokinetics and Pharmacodynamic labs (Visit 5 Day 15 only)
- 9) G100 (20 µg/lesion) administration (Note: If the injected tumor(s) regressed and is no longer of sufficient size for injection (either intra- or peritumoral) per evaluation by the investigator and there are no easily accessible alternate lesions – i.e., There are no longer any injectable lesions, the remaining G100 treatments and G100 only treatment visits may be cancelled. The patient should then continue with pembrolizumab and Clinical Assessment visits)
- 10) Urine pregnancy test on Day 14 prior to pembrolizumab. Note: For patients in UK and France, urine pregnancy tests must also be performed every month or sooner while the patient is receiving G100 and/or pembrolizumab.
- 11) On Day 14 and 35, administer pembrolizumab

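### The efficacy-evaluable set behind the Part 4 and Part 5 decision rules is defined in two conflicting ways, excludes the permitted 10 µg/lesion regimen in Part 4, and depends on exposure after enrolment

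*Protocol*

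**What the plan says.** **Part 4 (Protocol 14.2).** "For this analysis, 22 efficacy evaluable patients will be required". The set is defined by "Efficacy evaluable patients are patients who received at least 3 doses of G100 at 20" µg/lesion, at least one pembrolizumab dose, at least one post-baseline tumor assessment, and no major deviation that affects efficacy or its assessment. "With a target ORR of 40"%, 5 or fewer responders means futility, with a stated error of 7.2%. At a true ORR of 20% the stated stopping probability is 73.3%. The sponsor uses the result to decide on further development.

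**Part 5 (Protocol 14.2).** Evaluable patients "received at least 3 injections of G100 at the recommended dose and 3 doses of rituximab", with the same assessment and deviation conditions. Five or more CRs of 20 signal improvement over 10%. Stated power is 82% at a true CR rate of 32%, with 1-sided alpha 0.05.

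**Fallback dose.** The paragraph of Protocol 14.2 just before the Part 4 definition allows 10 µg if 20 µg/lesion "in a single lesion is not tolerated". Protocol 4.7 and 6.1 describe escalation at 10 µg/lesion in up to four lesions.

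**SAP.** Section 3.4 repeats both three-dose definitions. Section 4.3 defines the Efficacy Evaluable population by one injection, a baseline and a post-baseline assessment, and no major deviation. It names no dose level and assigns this set to the irRC response analysis. Section 5.6 adds a supportive analysis on the Safety population, which Section 4.2 limits to patients injected after local radiation.

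**Shrinking lesions.** Protocol 8.1.4: at the investigator's discretion, "should the G100 treated lesion(s) become too small or inaccessible for injection, G100 therapy will stop". Also: "As much of the full dose as possible should be given and the total dose of G100 administered should be recorded". Protocol 10.3.18 (Part 4): "There are no longer any injectable lesions, the remaining G100 treatments and G100 only treatment visits may be cancelled". Protocol 8.1.4 also allows another site to be chosen, and Protocol 6.1 for Part 4 continues injection around the regressed lesion.

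**The concern.** Each rule is a count out of a fixed number of evaluable patients, so its error rates are only as good as the definition of who counts. Three things undermine that definition.

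- One label carries two definitions. The SAP itself holds both, in Sections 3.4 and 4.3.
- A regimen that the protocol permits in Part 4 falls wholly outside the definition that accompanies the rule.
- The three-dose condition is met or failed after enrolment. A patient may fall short because lesions vanished, because of toxicity, or because the disease progressed. The first kind of exclusion removes likely responders, the other two likely non-responders.

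At stake is a development decision in Part 4 and a claimed activity signal in Part 5.

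**Working it through.** **1. Stated figures reproduced (exact binomial).**
- Part 4: P(X ≤ 5 | n = 22, p = 0.40) = 0.0722; P(X ≤ 5 | 22, 0.20) = 0.7326.
- Part 5: P(X ≥ 5 | 20, 0.32) = 0.8173; P(X ≥ 5 | 20, 0.10) = 0.0432.

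These match 7.2%, 73.3%, 82% and the 0.05 limit. The plan's arithmetic is right for a sample not selected on outcome.

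**2. The 10 µg/lesion branch (Part 4).** No calculation is needed. A patient treated only at 10 µg/lesion has zero doses at 20 µg/lesion and cannot reach three. Protocol 6.1 opens this branch after 2 or more DLTs in the first 20 µg cohort, which under 3+3 holds at most 6 patients. On that route the written definition could supply at most 6 of the 22 required. Under SAP 4.3 the same 10 µg patients would count.

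**3. Outcome-dependent exclusion.** Let r be the true rate, f the share of responders excluded and g the share of non-responders excluded, with enrolment continued to 22 or 20 evaluable. The rate in the evaluable set is

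r(1 − f) / [r(1 − f) + (1 − r)(1 − g)].

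Example, f = 10%, g = 0, r = 0.40: 0.36 / (0.36 + 0.60) = 0.375, and P(X ≤ 5 | 22, 0.375) = 0.111. Example, f = 0, g = 10%, r = 0.20: 0.20 / (0.20 + 0.72) = 0.217, and P(X ≤ 5 | 22, 0.217) = 0.660.

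The documents give no values for f or g. The values below are assumptions chosen to show sensitivity.

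| f | g | Part 4 false futility (ORR 40%) | Part 4 stop (ORR 20%) | Part 5 power (CR 32%) | Part 5 alpha (CR 10%) |
|---|---|---|---|---|---|
| 0 | 0 | 7.2% | 73.3% | 81.7% | 4.3% |
| 5% | 0 | 8.9% | 76.5% | 78.8% | 3.6% |
| 10% | 0 | 11.1% | 79.5% | 75.5% | 3.0% |
| 20% | 0 | 16.8% | 85.3% | 67.5% | 2.0% |
| 0 | 10% | 4.5% | 66.0% | 86.9% | 6.1% |
| 0 | 20% | 2.5% | 56.9% | 91.5% | 8.7% |
| 5% | 5% | 7.2% | 73.3% | 81.7% | 4.3% |
| 5% | 10% | 5.7% | 69.7% | 84.5% | 5.2% |

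Equal losses on both sides leave every figure unchanged. Unequal losses move the errors in whichever direction the larger loss dictates.

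**The case against.** A reader might infer that fast responders fall out of the count as a matter of course, so that the rules are biased against the treatment. The documents do not support that.

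- Protocol 10.3.18 and 10.3.25 allow cancellation only when nothing can be injected, in or around the tumor, and no easily accessible alternate exists. Protocol 8.1.4 and 6.1 otherwise redirect or continue injection.
- The third dose falls on Day 14 in both Parts. Neither Part uses radiation, and Part 4 pembrolizumab starts only on Day 14. Loss through regression is possible but narrow.

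Two further readings also fail. Nothing says that a partly delivered dose does not count: the DLT-evaluability rule asks for complete treatments, but the efficacy definition does not use that word. And the fallback gap is confined to Part 4, because the Part 5 criterion follows whatever dose is recommended.

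It is also fair to say that the fallback is optional and needs DMC agreement, that the protocol reports no DLTs at 20 µg in Parts 1 to 3, that both analyses are labelled exploratory, and that SAP Section 9 records termination of the study by the sponsor. These points lower the practical weight. They do not settle which definition governs, and they do not give the 10 µg branch an analysable set. The Safety-population analysis is an uncertain backstop, because its radiation condition, read literally, admits no Part 4 or Part 5 patient.

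**Conclusion.** The concern holds in this form. The conflict between SAP 4.3 and the three-dose definition in Protocol 14.2 and SAP 3.4 is on the face of the text, as is the absence of any evaluable patient treated only at 10 µg/lesion in Part 4. Neither rests on an assumption.

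The selection effect is real in principle but of unknown size and sign. With an assumed one-sided loss of 10%, Part 4 false futility is 11.1% rather than 7.2%, or stopping at 20% ORR is 66.0% rather than 73.3%. Part 5 power is 75.5% rather than 82%, or alpha is 6.1% rather than 4.3%. A claim that false stopping must rise, or that Part 5 power must fall, goes further than the documents allow: losing 5% of responders and 10% of non-responders gives 5.7% and 84.5%. These figures assume continued enrolment to the required evaluable number.

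**What to change.** Use one efficacy-evaluable definition in Protocol 14.2, SAP 3.4 and SAP 4.3, and say that it feeds both rules.

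- Refer to the protocol-permitted per-lesion dose assigned to the patient, not only to 20 µg/lesion.
- Do not exclude a patient for fewer than three G100 doses when the reason is regression, toxicity or progression. All three reasons must be covered; readmitting regression alone would select on a favourable outcome. The pembrolizumab and rituximab minimums need the same treatment, or they will keep some of the same patients out.
- State whether a partly delivered dose counts.

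Alternatively, keep the three-dose set and report both rules on all treated Part 4 and Part 5 patients as a sensitivity analysis, with the radiation condition in SAP 4.2 removed for these Parts. Fix the threshold in advance if more than 22 are treated. With 24 treated, for example, 5 or fewer gives 4.0% false futility at 40% ORR and 65.6% stopping at 20%; 6 or fewer gives 9.6% and 81.1%.

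Report 10 and 20 µg/lesion results descriptively by dose. Applying the 22-patient rule at each dose would need 22 evaluable patients at each. The statements in Protocol 6.1, 8.1.4 and 10.3.18 on what happens when a lesion regresses must also be reconciled.

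The cost is wording and one extra table. No patients or data are added, since the dose given is already recorded. With the study terminated, the SAP definition and the reporting are where the change still matters.
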